14.3 Analysis of Secondary Endpoints

Safety and tolerability data will be summarized by treatment group.

Adverse event rates will be coded by body system and MedDra classification term. Adverse events will be tabulated by treatment group and will include the number of patients for whom the event occurred, the rate of occurrence, and the severity and relationship to study drug.

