2 STUDY RATIONALE

This pilot study is a dose finding study to determine what dose of melatonin seems effective for treating acute migraine in children and adolescents with episodic migraine. We will identify the most effective dose to pull forward into a future fully-powered placebo-controlled efficacy study. If doses are equally effective, we will bring forward the best tolerated dose. If equally well tolerated, we will bring forward the lowest effective dose, as this will minimize cost to families should this treatment become widely adopted.

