8.3 Formulation of Test and Control Products

8.3.1 Formulation of Test Product

Chocolate melatonin pieces, developed by Good Day Chocolate

Table 1: Formulation of melatonin

	Melatonin
Active Ingredient, mg/mL	Melatonin 1mg per piece
Other ingredient, mg/mL	Chamomile extract

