8.3.3 Packaging and Labeling

Study drug is supplied in bulk from the manufacturer to the study team. The investigator team will place 1-8 pieces into each pill bottle, as determined by the randomization scheme. Each participant will receive two study treatment bottles—one for attack 1 and one for attack 2. The study team will label these bottles with the study ID number, and the attack they are intended for: i.e. “Attack 1” or “Attack 2” or “Extra” (in case they drop some or decide to treat a different attack). Participants randomized to receive either 1mg or 2mg will receive 4 extra pieces. Those randomized to 4mg or 8mg will get 8 extra pieces.,

Supply of Study Drug at the Site

Good Day Chocolate has donated the chocolate melatonin and the site will store it in a locked cabinet at room temperature.

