9.1.6 Adverse Events

Participants and parents will be able to report adverse events at any time during the study. Duration (start and stop dates and times), severity/grade, outcome, treatment and relation to study drug will be recorded on the case report form (CRF).

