10 EVALUATIONS BY VISIT

10.1 Visit 1

Baseline data will be collected by either an investigator and/or the study coordinator either in-person in the clinic, via a recommendation by their doctor or another member of the study team, or via phone for those enrolling remotely. All participants will have already been verified to meet ICHD criteria for episodic migraine. Headache duration, history, preventive medication use pattern, acute medication use pattern, aura status, family history, associated symptoms, comorbidities, pregnancy status and other variables will be assessed via questioning either in the clinic, chart review or via phone/text.

Participants will be instructed to treat two migraine attacks with their assigned melatonin dose. For those randomized to either 1mg or 2mg, they will receive 4 extra pieces in case they drop or lose any, or would like to use a different headache to track in the event that they take the melatonin and then something comes up where they are unable to track that headache for 24 hours.

For those randomized to 4mg or 8mg, they will receive 8 extra pieces. Participants are instructed that they are able to keep any unused pieces for a future attack but will be asked to return the empty bottles. Families will be asked to write down on the front cover of the headache diary how many of the extra pieces were either kept for later attacks, or were lost/dropped/thrown away. Alternatively, the study team will ask the families and record this for them. The diary asks how many chocolate pieces were taken for each attack.

Migraine attacks should be separated by at least 24 hours' headache freedom in between.

Participants will be provided with the Good Day sleep chocolate product and told their randomly assigned dose (either 1mg or 4mg for under 40kg, and either 2mg or 8mg for greater than or equal to 40kg). They will be given three bottles:

- Bottle 1 is labeled **Attack #1** and will have their exact dose (as described above)
- Bottle 2 is labeled **Attack #2** will have their exact dose (as described above)
- Bottle 3 is labeled **Extra** and will have either 4 or 8 pieces so they can have enough extra pieces if they drop or lose some of the pieces from bottle 1 or 2, as well as so they can use some if they want to treat another attack (they have been instructed to only use the dose they are assigned to)

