11 ADVERSE EXPERIENCE REPORTING AND DOCUMENTATION

11.1 Adverse Events

An adverse event (AE) is any untoward medical occurrence in a clinical investigation of a patient administered a pharmaceutical product and that does not necessarily have a causal relationship with the treatment. An AE is therefore any unfavorable and unintended sign (including an abnormal laboratory finding), symptom or disease temporally associated with the administration of an investigational product, whether or not related to that investigational product. An unexpected AE is one of a type not identified in nature, severity, or frequency in the current protocol or of greater severity or frequency than expected based on the information in the protocol.

The study team will collect AE information in the headache diary data. Adverse events will be recorded in the patient CRF. Adverse events will be described by severity, outcome, treatment and relation to study drug, or if unrelated, the cause.

AE Severity

The National Cancer Institute's Common Terminology Criteria for Adverse Events (CTCAE) Version 3.0 should be used to assess and grade AE severity, including laboratory abnormalities judged to be clinically significant. The modified criteria can be found in the study manual. If the experience is not covered in the modified criteria, the guidelines shown in

Table 1 below should be used to grade severity. It should be pointed out that the term "severe" is a measure of intensity and that a severe AE is not necessarily serious.

Table 1. AE Severity Grading

Severity (Toxicity Grade)	Description
Mild (1)	Transient or mild discomfort; no limitation in activity; no medical intervention or therapy required. The subject may be aware of the sign or symptom but tolerates it reasonably well.
Moderate (2)	Mild to moderate limitation in activity, no or minimal medical intervention/therapy required.
Severe (3)	Marked limitation in activity, medical intervention/therapy required, hospitalizations possible.
Life-threatening (4)	The subject is at risk of death due to the adverse experience as it occurred. This does not refer to an experience that hypothetically might have caused death if it were more severe.

AE Relationship to Study Drug

The relationship of an AE to the study drug should be assessed using the following the guidelines in Table 2.

Table 2. AE Relationship to Study Drug

Relationship to Drug	Comment

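### Tolerability, the tie-breaker between doses, is tabulated with no per-dose denominator or time window, although the number of doses taken can differ by arm

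*Combined protocol and SAP*

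**What the plan says.** Section 2 (and the synopsis, Study Design) gives tolerability a deciding role: "If doses are equally effective, we will bring forward the best tolerated dose". No margin is given for calling two doses equally well tolerated.

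Section 14.3 tabulates adverse events by treatment group. The table "will include the number of patients for whom the event occurred, the rate of occurrence, and the severity and relationship to study drug". The section does not say what the rate is divided by, or how long after a dose an event still counts. Section 9.1.6 sets no limit on reporting: "Participants and parents will be able to report adverse events at any time during the study". Section 11.1 names the main source: "The study team will collect AE information in the headache diary data". Under section 14, one dose is enough to enter the Safety Population.

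On exposure, sections 4.1 and 14.5 plan two treated attacks in every arm. Each participant also gets an Extra bottle. Section 8.3.1 gives the strength as "Melatonin 1mg per piece", and section 8.3.3 sets the extra supply: "Participants randomized to receive either 1mg or 2mg will receive 4 extra pieces. Those randomized to 4mg or 8mg will get 8 extra pieces". Section 10.1 supplies the extras partly "so they can use some if they want to treat another attack", and adds: "Participants are instructed that they are able to keep any unused pieces for a future attack". The diary records the pieces taken for each attack.

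**The concern.** The chance that a patient has at least one event rises with the number of doses that patient takes. A patient-level count is a fair comparison of two doses only if the arms take similar numbers of doses. Two features of the plan allow the numbers to differ:

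- **Completion.** A participant who treats one attack counts the same as one who treats two or more.
- **Extra supply.** In pieces, the high-dose arms receive more. In assigned doses, the low-dose arm of each weight stratum receives twice as many extras as its high-dose partner.

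A pilot of this size may well end without a clear efficacy difference, so the tie-breaker may be used. With no margin defined, a purely numerical gap in patients with events could choose the dose for the next trial. The distortion can also run the other way and hide a real difference in risk per dose.

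**Working it through.** The plan states no figure for tolerability, so there is none to reproduce. The arm size used below is the plan's own: 12 / (1 − 0.15 − 0.20) = 18.5, rounded up to 19, so 2 × 19 = 38 participants per dose level.

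**Step 1: doses available per participant.** Doses = 2 + extra pieces / pieces per assigned dose, at 1 mg per piece (8.3.1, 8.3.3).

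| Arm | Extra doses | Maximum doses |
|---|---|---|
| <40 kg, 1 mg (low) | 4/1 = 4 | 6 |
| <40 kg, 4 mg (high) | 8/4 = 2 | 4 |
| ≥40 kg, 2 mg (low) | 4/2 = 2 | 4 |
| ≥40 kg, 8 mg (high) | 8/8 = 1 | 3 |

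**Step 2: patients with at least one event.** Assume the same risk p per dose in every arm and independent doses. Then P = 1 − (1 − p)^k after k doses. At an assumed p = 10%:

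- k = 1: 10.0%
- k = 2: 19.0%
- k = 3: 27.1%
- k = 4: 34.4%
- k = 6: 46.9%

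Unequal completion alone, one dose against two, gives 10% against 19%.

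**Step 3: overall low against high, strata of equal size, p = 10%.** The same share of participants is assumed to use extras in every arm.

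- Exactly two doses each: 19.0% against 19.0%, gap 0.
- All supply used: low (46.9 + 34.4)/2 = 40.6%; high (34.4 + 27.1)/2 = 30.7%; gap 9.9 points, or about 15 against 12 patients of 38.
- Half use all extras, the rest take two doses: 0.5 × 9.9 = 4.9 points.
- A quarter do so: 0.25 × 9.9 = 2.5 points, or 38 × 0.025, about one patient.

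**Step 4: other values of p, all supply used.**

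| Risk per dose | Low | High | Gap (points) |
|---|---|---|---|
| 5% | 22.5% | 16.4% | 6.1 |
| 10% | 40.6% | 30.7% | 9.9 |
| 20% | 66.4% | 53.9% | 12.5 |
| 30% | 82.1% | 70.9% | 11.3 |

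**Step 5: masking.** With 10% risk per dose in the low arms, 14% in the high arms and all supply used, the high-dose figure is (1 − 0.86^4 + 1 − 0.86^3)/2 = (45.3 + 36.4)/2 = 40.8%, against 40.6% for low. At two doses each it would be 26.0% against 19.0%.

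**Step 6: the same data per dose.** With a per-dose denominator, equal risk per dose gives the same expected rate in every arm, whatever the number of doses taken.

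**The case against.** The strongest reply is that the plan already holds exposure roughly equal. Every arm is assigned two attacks, participation lasts until two are treated, and the diary named as the source of adverse events covers those two. The extras largely replace dropped pieces or serve a substitute headache, and pieces kept for later may be used after the study. Reaching the full-supply figures would need every participant to use every piece during the study, with events after undiaried doses captured as fully as the rest. This stands: those figures are a ceiling, not a forecast. Even there, the gap of 9.9 points is smaller than its standard error, √[(0.406 × 0.594 + 0.307 × 0.693)/38] ≈ 11 points. That does not remove the problem, because the selection rule requires no statistical test.

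A reader might infer that events have no link to dosing at all. The documents do not support that. Section 9.1.6 records when events begin and end and their relation to the study drug, section 11.1 brings timing after administration into the causality categories, and 14.3 tabulates relatedness. But a causality judgement, made here in an open-label trial, supplies no denominator.

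The rate in 14.3 might be intended per dose, and section 14 promises a SAP before the final analysis. Both are fair: the text is ambiguous rather than committed to a patient-level rate. As written, though, it does not settle the matter.

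**Conclusion.** The point holds as a gap in the analysis plan. Nothing in 14.3 adjusts for the number of doses taken, that number can differ by arm, and the result may decide which dose goes forward. The size is uncertain and could be nil. It depends on the risk per dose and the use of extras, neither of which the documents give, and on doses being independent. If use of extras is alike in all arms, the gap at 10% risk runs from 0 to about 10 points, against the low dose. Unequal completion is a separate route, whose direction depends on which arm completes less.

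Two stronger readings go too far. A reader might take 46.9% against 34.4% in children under 40 kg as the expected bias; it is the full-supply ceiling for that stratum. A reader might also infer that time enrolled will differ by arm and add unequal background events; allocation is randomised within weight strata, and the documents give no reason for enrolment time to depend on dose.

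**What to change.** In section 14.3, or the SAP promised in section 14:

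- **Main tolerability comparison.** Use the proportion of diary-recorded treated attacks with an adverse event starting within 24 hours of the dose, which is the diary's own follow-up span. Compare high with low dose overall by binomial GEE clustered on participant, with a small-sample correction.
- **By weight stratum.** Report descriptively. At 10% risk an arm would have about 19 × 2 × 0.10 = 3.8 events, too few for a reliable model. Overall there would be about 7.6 per dose level, so that estimate will be imprecise too.
- **Keep the patient-level table.** Show the number of treated attacks and doses taken per arm beside it.
- **List separately** events outside 24 hours or after undiaried doses.

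The limit to diary-recorded attacks matters. Counting undiaried doses in the denominator without equal capture of their events would lower the low-dose rate and could reverse the bias.

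The cost is SAP wording and one more table. Pieces per attack, side effects, event times and the fate of extra pieces are already collected (8.6, 9.1.6, 10.1). The downside is that late or undiaried events leave the main comparison, though they remain reported.

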14.4 Interim Analysis

There is no planned interim analysis.

14.5 Sample Size and Randomization

Participants will be randomized based on weight (over or under 40kg). Randomization will be in blocks of 4. Nineteen participants per arm will be randomized in each of the four treatment arms.

- 19 @ < 40 kg, given 1 mg at each of 2 attacks
- 19 @ < 40 kg given 4 mg at each of 2 attacks
- 19 @ ≥40 kg given 2 mg at each of 2 attacks
- 19 @ ≥40 kg given 8 mg at each of 2 attacks

15 DATA COLLECTION, RETENTION AND MONITORING

15.1 Data Collection Instruments

Data will be entered by the participant (headache diary) and by study staff (demographics, pill counts etc.). Subjects will not be identified by name in the study database, but by subject number. The study team will be responsible for data processing, in accordance with procedural documentation. Database lock will occur once quality assurance procedures have been completed.

Every effort will be made to keep participant data secure, though there is some risk of loss of privacy. The main privacy loss risk would be that it could be revealed than a child or adolescent has migraine and is taking a treatment for it. While sometimes migraine is stigmatized as being “just a headache” and the sufferer can be seen as a “complainer”, by being part of a medical research study on migraine treatment that might give legitimacy to the condition and thereby the sufferer.

15.2 Data Management Procedures

The data will be entered into a validated REDCap database. The study team will be responsible for data processing, in accordance with procedural documentation. Database lock will occur once quality assurance procedures have been completed.

All procedures for the handling and analysis of data will be conducted using good computing practices meeting FDA guidelines for the handling and analysis of data for clinical trials.

15.3 Data Quality Control and Reporting

After data have been entered into the study database, a system of computerized data validation checks will be implemented and applied to the database on a regular basis.

15.4 Archival of Data

The database is safeguarded against unauthorized access by established security procedures; appropriate backup copies of the database and related software files will be maintained. Databases are backed up by the database administrator in conjunction with any updates or changes to the database.

15.5 Availability and Retention of Investigational Records

The Investigator must make study data accessible to the IRB and Regulatory Agency (e.g., FDA) inspectors upon request. A file for each subject must be maintained that includes the signed Informed Consent, HIPAA Authorization and Assent Form and copies of all source documentation related to that subject. The Investigator must ensure the reliability and availability of source documents from which the information on the CRF was derived.

All study documents (patient files, signed informed consent forms, copies of CRFs, Study File Notebook, etc.) must be kept secured for a period of two years following marketing of the investigational product or for two years after centers have been notified that the IND has been discontinued.

15.6 Monitoring

Monitoring visits will be conducted by the investigator according to the U.S. CFR Title 21 Parts 50, 56, and 312 and ICH Guidelines for GCP (E6). By signing this protocol, the Investigator grants permission to appropriate regulatory authorities to conduct on-site monitoring and/or auditing of all appropriate study documentation.

15.7 Subject Confidentiality

In order to maintain subject confidentiality, only a subject number and subject initials will identify all study subjects on CRFs and other documentation submitted to the Sponsor. Additional subject confidentiality issues (if applicable) are covered in the Clinical Study Agreement.

16 ADMINISTRATIVE, ETHICAL, REGULATORY CONSIDERATIONS

The study will be conducted according to the Declaration of Helsinki, Protection of Human Volunteers (21 CFR 50), Institutional Review Boards (21 CFR 56), and Obligations of Clinical Investigators (21 CFR 312).

To maintain confidentiality, all laboratory specimens, evaluation forms, reports and other records will be identified by a coded number and initials only. All study records will be kept in a locked file cabinet and code sheets linking a patient's name to a patient identification number will be stored separately in another locked file cabinet. Clinical information will not be released without

written permission of the subject, except as necessary for monitoring by the FDA. The Investigator must also comply with all applicable privacy regulations (e.g., Health Insurance Portability and Accountability Act of 1996, EU Data Protection Directive 95/46/EC).

16.1 Protocol Amendments

Any amendment to the protocol will be written by the investigator. Protocol amendments cannot be implemented without prior written IRB approval except as necessary to eliminate immediate safety hazards to patients. A protocol amendment intended to eliminate an apparent immediate hazard to patients may be implemented immediately, provided the IRBs are notified within five working days.

16.2 Institutional Review Boards and Independent Ethics Committees

The protocol and consent form will be reviewed and approved by the UCSF IRB prior to study initiation. Serious adverse experiences regardless of causality will be reported to the IRB in accordance with the standard operating procedures and policies of the IRB, and the Investigator will keep the IRB informed as to the progress of the study. The Investigator will obtain assurance of IRB compliance with regulations.

Any documents that the IRB may need to fulfill its responsibilities (such as protocol, protocol amendments, consent forms, information concerning patient recruitment, payment or compensation procedures, or other pertinent information) will be submitted to the IRB. The IRB's written unconditional approval of the study protocol and the informed consent form will be in the possession of the Investigator before the study is initiated. The IRB's unconditional approval statement will be implemented by the Investigator prior to the shipment of study supplies to the site. This approval must refer to the study by exact protocol title and number and should identify the documents reviewed and the date of review.

Protocol and/or informed consent modifications or changes may not be initiated without prior written IRB approval except when necessary to eliminate immediate hazards to the patients or when the change(s) involves only logistical or administrative aspects of the study. Such modifications will be submitted to the IRB and written verification that the modification was submitted and subsequently approved should be obtained.

The IRB must be informed of revisions to other documents originally submitted for review; serious and/or unexpected adverse experiences occurring during the study in accordance with the standard operating procedures and policies of the IRB; new information that may affect adversely the safety of the patients of the conduct of the study; an annual update and/or request for re-approval; and when the study has been completed.

16.3 Informed Consent Form

Informed consent will be obtained in accordance with the Declaration of Helsinki, ICH GCP, US Code of Federal Regulations for Protection of Human Subjects (21 CFR 50.25[a,b], CFR 50.27, and CFR Part 56, Subpart A), the Health Insurance Portability and Accountability Act (HIPAA, if applicable), and local regulations.

The consent form generated by the Investigator must be approved by the IRB. The written consent document will embody the elements of informed consent as described in the International Conference on Harmonisation and will also comply with local regulations.

A properly executed, written, informed consent will be obtained from each subject's parent/guardian prior to entering the subject into the trial. Information should be given in both oral and written form and subjects (or their legal representatives) must be given ample opportunity to inquire about details of the study. Assent from the subject will also be obtained. If a subject is unable to sign the informed consent form (ICF) and the HIPAA authorization, a legal representative may sign for the subject. A copy of the signed consent form (and assent) will be given to the subject or legal representative of the subject and the original will be maintained with the subject's records.

164 Publications

The preparation and submittal for publication of manuscripts containing the study results shall be in accordance with a process determined by mutual agreement among the study investigators. The publication or presentation of any study results shall comply with all applicable privacy laws, including, but not limited to, the Health Insurance Portability and Accountability Act of 1996.

165 Investigator Responsibilities

By signing the Agreement of Investigator form, the Investigator agrees to:

1. Conduct the study in accordance with the protocol and only make changes after notifying the Sponsor (or designee), except when to protect the safety, rights or welfare of subjects.
2. Personally conduct or supervise the study (or investigation).
3. Ensure that the requirements relating to obtaining informed consent and IRB review and approval meet federal guidelines, as stated in § 21 CFR, parts 50 and 56.
4. Report to the Sponsor or designee any AEs that occur in the course of the study, in accordance with §21 CFR 312.64.
